7.5 Post-Procedure / Hospital Discharge

- Investigator satisfaction with the MSS's ability to retract intended tissues and facilitate visualization and access of the surgical site

Before hospital discharge the following data will be collected:

- Length of hospital stay (time from admittance to post-anesthesia care unit until hospital discharge)
- Length of time spent in Post Anesthesia Care Unit (PACU)
- SSI
- Adverse events, if any

7.6 Follow-up

All subjects will be asked to return to the investigational site at 7 days and again at 30 days post-procedure according to the study schedule described in **Table 1**. Subjects will be queried about satisfaction with the MSS facilitated procedure at the 30 day visit and about adverse events at both study visits. Study visits should be scheduled as closely as possible to the earlier part of the visit window to allow for rescheduling if needed due to last minute schedule changes. Visits not completed within the specified visit window will be regarded as protocol deviations.

Table 1: Schedule of Assessments

Assessment	Time Frame			
	Pre-op Baseline	Index Procedure	7 day follow-up	30 day follow-up
Visit Window	- 30 days	NA	± 3 days	± 7 days
Informed Consent	√			
Medical History	√			
Demographics	√			
Blood Tests	√			
Pregnancy Test *	√	√		
Intra-operative assessments		√		
Adverse events		√	√	√
Investigator satisfaction		√		
Subject satisfaction				√

* Urine pregnancy test for all women of childbearing potential at pre-op visit and repeated within 7 days of index procedure unless pre-op visit/prior urine pregnancy test was within 7 days of index procedure.

7.7 Unplanned Follow-up Visits

Subjects returning for unscheduled visits will be reported on the Unscheduled Visit case report form.

7.8 Early Discontinuation / Withdrawal

All subjects will be informed of their right to withdraw from the clinical study at any time without penalty or loss of benefits to which the subject is otherwise entitled. Additionally, the Investigator may prematurely discontinue any subject's participation in the study if the Investigator believes that the subject can no longer fully comply with the requirements of the study or if any of the study procedures are deemed potentially harmful to the subject. The reason for early discontinuation will be documented in the source documents and the Study Termination case report form.

7.9 Lost to Follow-up Subjects

Every attempt will be made to have all subjects complete the follow-up visit schedule. A subject will not be considered lost to follow-up unless efforts to obtain compliance are unsuccessful. At a minimum, the effort to obtain follow-up information will include three attempts to make contact via telephone or email and if unsuccessful, then a certified letter from the Investigator will be sent to the subject's last known address. In general, the study Site Coordinator should attempt to contact the subject after each missed visit to reschedule the visit.

8 RISK / BENEFIT ANALYSIS

8.1 Benefits

Possible benefits of the Levita Magnetic Surgical System are a reduction in the number of surgical ports needed to perform the surgery, with associated reduction in post-operative pain and scarring, a shorter length of stay in the hospital, and a faster recovery.

8.2 Risks

There are risks associated with use of the Levita Magnetic Surgical System including:

- Electromagnetic field incompatibility or interference
- Malfunctioning of the device
- Breakage of the device
- Allergic reaction related to the device
- Abdominal wall/cavity/tissue and/or organ injury or damage (e.g. inflammation, redness)
- Infection
- Tissue damage, including hematoma, bleeding or petechiae
- Vascular injury
- Gastro-intestinal injury
- Organ perforation
- Need for extended surgery
- Additional surgical intervention due to any of the above factors (includes reoperation)

These adverse events do not include all adverse events, which occur with surgery in general, but are important considerations particular to laparoscopic instrumentation.

8.3 Minimization of Risk and Monitoring Procedures

The MSS has been evaluated in clinical studies of cholecystectomy, bariatric surgery, and prostatectomy and has been in commercial distribution for over two years.

Risks are mitigated in this clinical study through selection of qualified physicians with competence in minimally invasive surgery, appropriate training, and study monitoring.

- Investigators who participate in the study will be experienced and skilled in laparoscopic surgical techniques. Additionally, Investigators, in conjunction with the investigational site, will have adequate resources for participation in a clinical study.
- The study has been designed to ensure treatment and follow-up of subjects are consistent with current medical practice.

- Each Investigator will ensure oversight and approval of the study by the Ethics Committee (EC) prior to initiation of the clinical study at his/her investigational site.
- The Investigator and study personnel will be trained on the clinical protocol.
- All Investigators will undergo training prior to first use during the clinical study.
- All Investigators and Operating Room (OR) support personnel will be provided with an IFU during training and as a reference for review as needed.
 - The IFU details appropriate safe working zones for use of the Magnetic Controller in an OR setting and considerations for users of a product with a strong magnet.
- Study personnel are also trained with and receive a “Magnetic Surgery Screening Checklist” and OR signage to ensure safe use of the system for subjects and users.
- Subjects will be carefully evaluated against the inclusion/exclusion criteria prior to entering the clinical study to ensure that their diagnosis and medical status are appropriate for participation in the clinical study.
- Subjects will be monitored up to the 30-day follow-up visit as defined in the study protocol. The follow-up visit will be with an Investigator to monitor the subjects’ status.
- A study Investigator will evaluate the subject for any adverse events potentially related to the device.
- Data from the investigative sites will be monitored throughout the study. Monitoring visits will be conducted at the investigative sites at the initiation of the study and periodically throughout the study to evaluate protocol compliance and to determine if there are any issues that may affect the safety or welfare of the subjects.

9 STATISTICAL SECTION

9.1 Statistical Methods

Data collected in the study will be presented using various descriptive statistics. Descriptive summaries will be the basis of study reports to generate an overall summary of the safety and effectiveness for the device.

Descriptive tables will be produced for baseline characteristics including demographics and medical history.

Missing data on study endpoints will be described.

9.2 Sample Size Justification

This is a single-arm, multicenter, investigational study. No formal sample size estimation has been performed. As safety and effectiveness have already been demonstrated in several prior indications (laparoscopic

cholecystectomy, bariatric and prostate procedures), it is expected that enrollment of 30 subjects will provide ample evidence of safe and effective use of the MSS in this additional subject population.

10 DATA MANAGEMENT

10.1 Data Collection

Data will be collected on paper case report forms (CRF) supplied by the Sponsor. The Site Principal Investigator is responsible for the accuracy and completeness of all study documentation.

Corrections to the CRF must be corrected by drawing a single line through the incorrect data, entering the correct data beside the incorrect entry, then initialing and dating the correction. Incorrect data must not be obscured. The use of pencil, erasable ink, or correction fluid on CRFs is prohibited. All fields must be completed, e.g. if the item was not done, mark "N/D". If the item is not applicable to an individual case, mark the field "N/A".

CRFs will be printed on 3-part NCR paper (or equivalent) so that both the site and monitor/Sponsor will have copies of the CRFs. The second copy may be sent to the Sponsor for remote monitoring. Any other subject information sent to the Sponsor must be redacted of personal identification information.

A unique study number will be assigned to each subject. All information recorded on the CRF about the subject will be recorded with the study number on it. The main database will contain only the study number to identify the subject. The code with subject name and study number will be maintained in a secured designated location at the site and will be inspected by study monitors and auditors. Any computerized data will be password protected.

The Sponsor will be responsible for database design and management.

10.2 Data Processing

Monitoring, described below, will be completed prior to data entry. In association with data entry, the data will be reviewed for further inconsistencies or incongruities. If warranted, a data clarification form or communication will be used to query the Investigator. Data will be either 100% audited or double data entry will be used to ensure accurate and complete study information.

11 MONITORING AND QUALITY CONTROL PROCEDURES

11.1 Control of Systemic Error/ Bias

Clinical monitors will verify subject data and ensure compliance with Good Clinical Practices (GCPs), clinical protocol and other study requirements. As

detailed in Section 13, an Independent Physician will adjudicate all adverse events for relatedness, severity, and seriousness. The adjudication results will be used for purposes of data analysis. The Site Investigator's analysis will also be presented in the final clinical study report.

11.2 Monitoring and Auditing

Monitoring visits to the clinical sites will be made periodically during the study, to ensure that all aspects of the current, approved protocol/amendment(s) are followed.

Prior to the enrollment of any subject in this study, site study personnel will be trained to Good Clinical Practice, the protocol and the device including Instructions For Use and management of a magnetic device. Additionally, the procedure for obtaining informed consent and the procedure for reporting adverse events will be reviewed.

Site monitoring visits will be performed by the Monitor on a regular basis during which case report forms will be 100% verified against source documentation. Data will be reviewed for safety information, legibility, completeness, accuracy, and logical consistency. Additional computer programs (e.g. edit checks) that identify selected protocol violations, out-of-range data, and other data errors may be used to help monitor the trial. Investigators will be required to make corrections to any data errors.

The Monitor is responsible for ensuring, through personal contact with the Investigator and site personnel, that the members of the clinical staff clearly understand and accept the obligations incurred in this investigation, and that these obligations are being fulfilled throughout the study. Specifically, the Monitor will interact with the site via telephone contact and periodic on-site visits to ensure that:

- Study facilities continue to be acceptable for the conduct of the study
- Regulatory and study documents are complete and current
- The protocol is appropriately followed
- Protocol amendments have been approved by the EC and the local regulatory authorities (as applicable), and the Sponsor has received the approval in writing
- Qualified subjects are enrolled in a timely manner
- Accurate, complete, and current records are maintained for all subjects
- The information recorded and submitted to the Sponsor is representative of the subject record and other supporting documentation
- Inconsistent and incomplete data are addressed and resolved
- Accurate, complete, and timely adverse event reports are being made to the Sponsor
- The site Principal Investigator continues to assume primary responsibility for the study
- Study devices are properly stored, dispensed, and accounted for

The Investigator or designee must, upon request, provide to the Monitor or regulatory authority the necessary study records for a thorough review of the study's progress. These records include, but are not limited to, case report forms and original documents and records such as hospital and clinic charts, consent forms, laboratory records, and pharmacy dispensing records.

The Monitor will provide a written report to the Sponsor after each on-site visit. The report will identify the personnel participating in the visit, the activities performed, any protocol deviations, and any action items/corrective actions identified.

If compliance problems or protocol deviations are noted, the Sponsor will recommend corrective action. If the response from the Investigator is not adequate, the Sponsor will terminate the site's participation in the study and notify the regulatory authorities (if applicable).

The study may also be subject to a quality assurance audit by the Sponsor or its designees, as well as inspection by appropriate regulatory authorities.

It is important that the Investigator and relevant study personnel are available during the monitoring visits and possible audits and that sufficient time is devoted to the process.

11.3 Device Accountability

Study devices must be used according to the protocol, Instructions for Use and Training.

The site Principal Investigator or an authorized designee shall keep records documenting the use of the study device by indicating the lot number on each subject's case report form.

12 ADVERSE EVENTS

12.1 Definitions

12.1.1 Adverse Event (AE)

AEs are any untoward medical occurrence, unintended disease or injury, or untoward clinical signs (including abnormal laboratory findings) in which subjects, users or other persons, whether or not related to the study medical device. This definition includes events related to the procedures involved. For users or other persons, this definition is restricted to events related to study medical devices.

All adverse events, regardless of relationship to the device, must be recorded on the case report forms provided. Adverse events that occur during this study should be treated by established standards of care.

Adverse events shall be assessed and documented at the time of the procedure and at all study follow-up visits. Each Investigator shall provide source documentation as requested by the Sponsor to facilitate reporting and adjudication of these events.

12.1.2 Serious Adverse Event (SAE)

An adverse event is considered a SAE if it:

- Led to death
- Led to a serious deterioration in the health of the subject, that either resulted in:
 - a) A life-threatening illness or injury, or
 - b) A permanent impairment of a body structure or a body function, or
 - c) In-patient hospitalization, or prolongation of existing hospitalization, or
 - d) medical or surgical intervention to prevent permanent life-threatening illness or injury or permanent impairment to body structure or a body function.
- Led to fetal distress, fetal death or a congenital abnormality

Planned hospitalization for a pre-existing condition, without serious deterioration in health, is not considered a serious adverse event.

12.1.3 Serious Adverse Device Effect (SADE)

A serious adverse device effect is defined as an adverse event related to the use of an study medical device that has resulted in any of the consequences characteristic of a serious adverse event.

12.1.4 Unanticipated Serious Adverse Device Effect (USADE)

An USADE is a serious adverse device effect which by its nature, incidence, severity or outcome has not been identified in the current version of the investigational plan.

12.2 Adverse Event Reporting

Any adverse event that occurs during the course of the study must be reported using the Adverse Event (AE) Form in the CRFs and the Investigator must sign each report. The Investigator must determine whether the adverse event is serious or unanticipated, its intensity, and the relationship of each adverse event to the study device or procedure. As noted in Section 13, an Independent Physician Adjudicator will also adjudicate all AE data.

Pre-existing medical conditions or symptoms occurring prior to the laparoscopic procedure involving the Levita MSS should not be reported as adverse events, unless there is a worsening of the pre-existing medical condition.

All serious adverse events, including unanticipated serious adverse device effects, must be reported to the Sponsor within 24 hours of the site first becoming aware of the event via email ([contact]). At a minimum, the AE CRF should be provisionally completed, scanned and sent via email. The Sponsor will contact the site for additional information, if required.

For any adverse event that is ongoing at the time of the initial report, periodic follow-up information is required until the adverse event is resolved or is not expected to change. The site should submit relevant follow-up information related to the adverse event as soon as it is available.

Depending upon the nature and seriousness of the adverse event, the Sponsor may request the Investigator to provide copies of the subject's medical records (such as the subject's laboratory tests and hospital records, Investigator summaries, etc.) to document the adverse event. The Sponsor and/or Sponsor designated clinical/medical personnel are available to respond to any medical issues that arise during the conduct of this study.

The Investigator will report all serious adverse events, including unanticipated serious adverse device effects, to the EC according to the EC requirements. A copy of this EC communication should be sent to the Sponsor.

Within 10 working days of notification, the Sponsor will report all unanticipated adverse device effects to the appropriate authority, all participating Investigators, and all reviewing ECs. The Sponsor will ensure that safety reporting for the study is conducted in compliance with all pertinent requirements and regulations.

12.3 Adverse Event Severity

The Investigator must determine the severity of the adverse event according to the following definitions:

Mild The adverse event is noticeable to the subject, but does not interfere with routine activity; the symptoms are easily tolerated and transient in nature.

Moderate The adverse event interferes with routine activity but responds to symptomatic therapy or rest; the symptoms are poorly tolerated and sustained.

Severe The adverse event significantly limits the subject's ability to perform routine activities despite symptomatic therapy. The adverse event requires

medical or surgical treatment or results in hospitalization.

Life-Threatening The subject is at immediate risk of death.

12.4 Event Relationship

The following lists the potential event attribution categories.

12.4.1 Device Related

An adverse event is considered device-related when the clinical event has a reasonable time sequence associated with use of the study device and is unlikely to be attributed to concurrent disease or other procedures or medications. It is reasonable to believe that the device directly caused or contributed to the adverse event.

The Investigator will evaluate the relationship of the adverse event to the Levita MSS according to the following definitions:

Definite The adverse event is clearly related to the study device: the event has a temporal relationship to the study device, follows a known pattern of response, or is otherwise logically related to the study device, and no alternative cause is present.

Probable The adverse event is likely related to the study device: the event has a temporal relationship to the study device, follows a known or suspected pattern of response, or is otherwise logically related to the study device, but an alternative cause may be present.

Not likely The adverse event is unlikely related to the study device: the event does not follow a clear temporal relationship to the study device or does not follow a known pattern of response, or is otherwise likely to be due to the subject's clinical state or other modes of therapy.

Not related The adverse event is clearly not related to the study device: the event has no temporal or other relationship to the administration of the study device, follows no known or suspected pattern of response, and an alternative cause is present.

Unknown Unable to determine the relationship based on all available information.

12.4.2 Procedure-Related

An adverse event is considered to be procedure-related when it is reasonable to believe that the event is associated with the index procedure and is not specific to the study device. Other products,

surgical techniques, or medications required specifically for the procedure may have contributed to the occurrence of the event.

The Investigator will evaluate the relationship of the adverse event to the procedure according to the following definitions:

Definite The adverse event is clearly related to the procedure: the event has a temporal relationship to the procedure, follows a known pattern of response, or is otherwise logically related to the procedure, and no alternative cause is present.

Probable The adverse event is likely related to the procedure: the event has a temporal relationship to the procedure, follows a known or suspected pattern of response, or is otherwise logically related to the procedure, but an alternative cause may be present.

Not likely The adverse event is unlikely related to the procedure: the event does not follow a clear temporal relationship to the procedure or does not follow a known pattern of response, or is otherwise likely to be due to the subject's clinical state or other modes of therapy.

Not related The adverse event is clearly not related to the procedure: the event has no temporal or other relationship to the procedure, follows no known or suspected pattern of response, and an alternative cause is present.

Unknown Unable to determine the relationship based on all available information.

12.5 Subject Death

Any subject death during the investigation must be reported to the Sponsor within 24 hours of Investigator's knowledge of the death. The Adverse Event CRF must be completed and include a complete description of the relevant details of the death. A copy of the death records, death certificates and an autopsy report (if performed) are required to be sent to the Sponsor. In addition, subject death must be reported to the EC in accordance with EC requirements.

12.6 Device Deficiency

All device deficiencies related to the identity, quality, durability, reliability, safety or performance (includes malfunctions, use errors, and inadequate labeling) of the device shall be documented. Sponsor will assess all device

deficiencies that could have led to a serious adverse device effect for potential regulatory reporting requirements.

In the event of a suspected malfunction or device deficiency, the study device should be returned to the Sponsor for analysis. Instructions for returning the study device will be provided by the Sponsor.

13 STUDY OVERSIGHT

13.1 Physician Adjudicator

An Independent Physician Adjudicator will be responsible for the adjudication of all reported adverse events. The Independent Physician Adjudicator will be a General Surgeon familiar with laparoscopic surgery who is not an Investigator in the trial and does not have a financial conflict of interest with the Sponsor. The adjudication process will include determination of device and procedure relatedness, seriousness, and severity of the adverse event. If there is insufficient evidence to make these determinations, the Physician Adjudicator may choose to request additional information. All available data will be presented for review to the Independent Physician Adjudicator.

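### The protocol gives the single adjudicator all available data and nowhere withholds the Investigator's own ratings, so the adjudication relied on to control bias is not protected against anchoring

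*Combined protocol and SAP*

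**What the plan says.** The protocol describes two assessments of each adverse event.

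- **Investigator.** Under 12.2, any adverse event "must be reported using the Adverse Event (AE) Form in the CRFs and the Investigator must sign each report". The same section says: "The Investigator must determine whether the adverse event is serious or unanticipated, its intensity, and the relationship of each adverse event to the study device". A rating against the procedure is required as well. Sections 12.3 and 12.4 give the scales.
- **Adjudicator.** Section 12.2 adds that "an Independent Physician Adjudicator will also adjudicate all AE data". Section 13.1 sets the scope: "The adjudication process will include determination of device and procedure relatedness, seriousness, and severity of the adverse event". It also describes what this person is shown: "All available data will be presented for review to the Independent Physician Adjudicator".

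On independence, 13.1 requires a general surgeon familiar with laparoscopy "who is not an Investigator in the trial and does not have a financial conflict of interest with the Sponsor". These conditions concern who the adjudicator is. They do not concern what the adjudicator sees.

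Section 11.1, under the heading on systematic error and bias, names this adjudication as a safeguard and says: "The adjudication results will be used for purposes of data analysis". It adds that the site's assessment will appear in the final report as well.

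**The concern.** An independent second reading controls bias to the extent that the second reader reaches a view without the first reader's answer. Here the second reader rates the attributes that the Investigator has already rated. The plan states no masking, no first reading without the site's ratings and no list of what goes into the file.

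At stake is the classification of events in the primary safety endpoint, which section 5.1 summarises by relatedness, seriousness and severity. The study is single-arm and open label (6.1), so no comparator rate could show that events were being attributed wrongly. One person adjudicates, and no second adjudicator or consensus step is described. Section 14.11 allows the results to support regulatory submissions.

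**Working it through.** The plan gives no figure on this point, so the check is a comparison of sections.

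**1. Do the two assessors rate the same things?**

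| Attribute | Investigator | Adjudicator (13.1) | Safety summary (5.1) |
|---|---|---|---|
| Device relatedness | Yes (12.2, 12.4.1) | Yes | Yes |
| Procedure relatedness | Yes (12.2, 12.4.2) | Yes | Yes |
| Seriousness | Yes (12.2, 12.1.2) | Yes | Yes |
| Severity | Yes (12.2, 12.3) | Yes | Yes |
| Unanticipated | Yes (12.2) | Not listed | Not listed |

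The overlap is complete on every attribute that enters the endpoint. The last row matters as well. By 12.1.3 and 12.1.4, an unanticipated serious adverse device effect is by definition both serious and device-related, so a site entry to that effect would give away two of the other ratings.

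**2. Are the Investigator's ratings within what the adjudicator is shown?** Section 13.1 sets no exclusion, and 12.2 speaks of adjudicating all the adverse event data directly after listing the Investigator's determinations. Disclosure is the natural reading. It is not an express statement: the layout of the form is not in the document, and no order of reading is given.

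**3. Does anything else keep the two readings apart?** Section 12.1.1 lets the Sponsor obtain source documentation for adjudication, 13.1 lets the adjudicator ask for more, and 7.4 provides for video of the procedure. All of these improve the evidence. None removes an answer that has already been seen.

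**4. What would the two reported assessments show?** Disagreement would be visible and informative. Agreement would fit two explanations equally well: two readers independently reached the same view, or the second followed the first. Without masking, the report cannot tell these apart.

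**5. Which attributes are most exposed?** Seriousness rests on listed outcomes (12.1.2) and leaves less room for judgement. Relatedness leaves more. In 12.4.1, *Probable* admits a possible alternative cause and the next category down is *Not likely*, with nothing between them. Several device risks in 8.2, such as infection, bleeding and organ perforation, could also follow from the operation itself.

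**6. Can the effect be sized?** No. The plan gives no expected event rate, no expected rate of agreement and no success threshold. Analysis is descriptive (9.1), and no formal sample size calculation was made (9.2).

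**The case against.** The strongest reply is that the plan contradicts nothing: it never promises masked adjudication. The sentence in 13.1 follows one about insufficient evidence, so it can be read as a guarantee of complete evidence and not as a rule on what is seen first. The adjudicator is a qualified surgeon without a financial conflict. Case report forms are verified in full against source (11.2), and both assessments are published. Every event is recorded whatever its cause (12.1.1), so a swayed rating moves an event between categories and does not remove it. Sending everything also prevents the Sponsor from choosing what the adjudicator sees.

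Most of this stands, and it limits the point to classification. It does not supply the missing safeguard, because a guarantee of complete evidence is compatible with withholding the ratings. The worry about Sponsor selection is a reason to keep redaction narrow.

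Three stronger readings are tempting, and the documents support none of them.

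- *The adjudication is anchored.* That states a risk as a fact. The text shows only that protection is absent.
- *The operating surgeon's own verdict is what is shown.* The Investigator operates (7.4), but under 8.3 a study Investigator evaluates events, who need not be the one who operated on that subject.
- *Each reclassified subject shifts the device-related proportion by 1/30 = 3.3 percentage points.* The arithmetic is right for 30 subjects. However, the plan defines no such proportion and no cut between *Probable* and *Not likely* for analysis, and anchoring could raise relatedness as well as lower it.

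**Conclusion.** The concern holds as a missing safeguard in the procedure that section 11.1 relies on for bias control. The adjudicated classification is the one analysed, and nothing in the protocol stops the single adjudicator from seeing the Investigator's classification first. Agreement between the two could therefore not be offered as evidence of independence.

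The consequence is limited to how events are distributed across relatedness, seriousness and severity in the primary safety summary. The capture of events is unaffected, and no test or decision threshold depends on the result. Neither the direction nor the size of any effect can be derived from the documents.

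The conclusion assumes that the all-data wording in 13.1 includes the completed adverse event form, and that no separate adjudication procedure masks the ratings. If such a procedure exists, citing it in 13.1 would settle the point.

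**What to change.** Amend 13.1 to set the order of reading:

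1. The adjudicator receives all clinical evidence: the event narrative, source records and relevant procedure video.
2. The Investigator's rating fields on the adverse event form are masked. There are five: device relatedness, procedure relatedness, seriousness, severity and the unanticipated entry.
3. The adjudicator records a determination. Only then may the site's classification be seen.
4. The final report gives the agreement between the two assessments, alongside the site's own analysis that 11.1 already promises.

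State in the amendment that redaction is confined to those rating fields, so that no clinical evidence is withheld and the Sponsor gains no discretion over the file.

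The cost is a small redaction step on multipart paper forms (10.1) and possibly a few more queries from the adjudicator. Masking will be incomplete where source records themselves comment on attribution, and the report should say so. Expedited reporting by the sites is untouched, and no subject procedure or change in sample size is involved.
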